4.9 Data collection

Data collection is performed partly through the eCRF, partly through the Swedish Colorectal Cancer Registry (SCRCR) and other Swedish national registries (for Swedish subjects), and partly through separate data collections directly from trial sites (subjects in other Nordic countries). Baseline characteristics that are collected from the SCRCR for Swedish subjects are collected separately from each site for the Nordic countries outside of Sweden. Table 5 contains information on data sources for subjects in Sweden and other Nordic countries. Each data source is described in the below subsections (4.9.1, 4.9.2, 4.9.3, 4.9.4, and 4.9.6). Note that some variables are collected from several data sources, e.g. the pathological tumor-node-metastasis (pTNM) stage and cancer location. For such variables, data from the eCRF will be preferred, with the exception of data from the Department of Medical Epidemiology and Biostatistics (MEB) (see subsection 4.9.6 for details), since the eCRF is regularly monitored (see Section 4.10), but data from other sources can be used if there are data missing from the eCRF.

Table 5. Data sources for the ALASCCA clinical trial, for randomized subjects.

Variable	Sweden	Denmark, Finland, Norway
- Inclusion and exclusion criteria	eCRF	eCRF
- Mutation type (blinded) (PIK3CA (exon		
9/20) or PTEN/PIK3R1/PIK3CA (other		
exons))		
- Randomized group		
- Age at screening visit 2		
- Date of surgery		
- Sex		
- pTNM stage		
 Cancer location (colon/rectum) 		
- Compliance		
 Concomitant medication 		
- CT/MRI at 12 and 36 months		
- AEs		
Endpoint variables assessed at 3 years for	eCRF	eCRF
ubjects reaching a study endpoint or		
ompleting 3 years in the trial:		
 CRC recurrence within 3 years (local and distant) 		
- Other cancer within 3 years		
- Death within 3 years		
- CEA level (if applicable)		
- Date of 3-year follow-up CT		
additional endpoint variables assessed at 3	Collected separately	Collected separately
ears for all subjects:	from sites/SCRCR	from sites
 CRC recurrence, and corresponding date 		
 Location(s) of CRC recurrence (local/liver/lung/other) 		
 Other cancer, and type of other cancer, within 3 years, and corresponding date 		
- Death within 3 years, and corresponding date		
- Date of last known to be alive		
- CEA level (if applicable)		
- Date of 3-year follow-up CT		
Endpoint variables assessed at 5 years for	eCRF	eCRF
subjects reaching who completed 3 years in		
ne trial:		
- CRC recurrence within 5 years (local		
and distant)		
- Death within 5 years		
- ASA treatment after end of trial (assessed at 5 years)		
- CEA level (if applicable)		
Indpoint variables assessed at 5 years for	SCRCR/Collected	Collected separately
ubjects leaving the trial before study	separately from sites	from sites
ompletion/death:		
 CRC recurrence yes/no and date of recurrence or date of last known to be without CRC recurrence 		

Variable	Sweden	Denmark, Finland, Norway
Death yes/no and date of death or date of last known to be alive		
ASA treatment after end of trial (assessed at 5 years)	PDR	Not collected
SAEs	eCRF (and reported on paper directly to trial coordinator)	eCRF (and reported on paper directly to trial coordinator)
Treatment and cancer specific variables at baseline:	SCRCR	Collected separately from sites
 Date of CRC diagnosis Body mass index (BMI) ASA Score Tumor location Tumor location in colon cancer Height from anal verge (rectal cancer) Neoadjuvant radiotherapy (RT) (yes/no) Neoadjuvant chemotherapy (yes/no) Neoadjuvant chemoradiotherapy (CRT) (yes/no) Elective/emergency surgery Type of surgery pTNM stage Tumor differentiation Adjuvant chemotherapy (yes/no) 		
Oncological treatment - Type of neoadjuvant and adjuvant treatment (None, Only RT, CRT, RT+Chemotherapy, CRT+Chemotherapy, Only Chemotherapy) - Total dose, number of fractions, and start date of neoadjuvant and adjuvant RT - Start date and type of neoadjuvant and adjuvant chemotherapy	SCRCR/Collected separately from sites	Collected separately from sites
Other tumor mutations (MSI-status, BRAF, KRAS, NRAS)	Extracted from MEB database	Extracted from MEB database

4.9.1 Electronic Case Report Forms (eCRFs)

The eCRF is integrated with INCA – a national IT platform for Swedish quality registries. Study personnel at the study sites have secure login credentials to access and enter subject data into the eCRF system.

4.9.2 Swedish Colorectal Cancer Registry (SCRCR)

All Swedish CRC cases are reported to the SCRCR, which includes patient, tumor, and treatment specific factors. Several baseline variables, and some endpoint variables (see Section 4.9.4), for the randomized Swedish subjects will be collected from the SCRCR, see Table 5.

4.9.3 Additional baseline data for Nordic countries outside of Sweden

Data on patient, tumor, and treatment specific variables from subjects from the Nordic countries outside of Sweden are not part of the SCRCR. These data are collected separately from each included site using standardized forms in xlsx-format. The data will be merged with the Swedish data extracted from the SCRCR.

4.9.4 Additional collection of endpoint variables

Endpoint variables assessed at 3 years from randomization for subjects leaving the trial before trial completion, CRC recurrence, other cancer, or death, are not entered into the eCRF. Date and location(s) (local/liver/lung/other) of CRC recurrence, other cancer and death, or dates for which a subject is last known to be without such events, will be collected separately from all sites, including the Swedish sites. For subjects experiencing CRC recurrence, sites will be asked to provide information on date and location(s) (local/liver/lung/other) of CRC recurrence. For subjects completing the trial without any registration of CRC recurrence/other cancer/death in the eCRF or SCRCR (for Swedish subjects), sites will be asked to review the medical charts and provide any information on endpoint variables that has not been entered into the eCRF. Each site will be asked to provide the additional 3-year endpoint data when 3 years have elapsed since their last subject was randomized.

Endpoint variables assessed at 5 years from randomization for subjects leaving the trial before trial completion are not entered into the eCRF. Date of CRC recurrence, other cancer, and/or death, or dates for which a subject is last known to be without such events, will be collected from SCRCR for Swedish subjects, and from each included site for subjects in Nordic countries outside of Sweden. Data on ASA treatment after the IMP part of the trial until 5 years after randomization will be collected from the Swedish Prescribed Drug Register (PDR) for Swedish subjects.

4.9.5 Additional collection of oncological treatment

Type and details of neoadjuvant and adjuvant oncological treatment, including start dates of RT and chemotherapy, RT total doses and number of fractions, and substances given in chemotherapy, are collected from the SCRCR (if registered) and separately from each trial site.

4.9.6 Data on tumor mutations

Tumor cell DNA is extracted from tumor samples at the Karolinska Institutet Biobank, and a pre-specified set of genes are sequenced at Clinical Genomics, SciLife Lab. The sequencing data are analyzed by bioinformaticians at MEB, KI. Data containing study ID, somatic alterations in PIK3CA exon 9/20 (Mutation A: PIK3CA exon 9 and 20 hotspot small mutations), other PIK3CA/PIK3R1/PTEN (Mutation B: other PIK3CA, PIK3R1 and PTEN non-silent small mutations and focal/homozygous deletion of PTEN), microsatellite instability (MSI), and KRAS, BRAF, NRAS mutation status will be extracted from the database at MEB. Whether a subject has somatic alterations in PIK3CA (Mutation A), PIK3CA/PIK3R1/PTEN (Mutation B), or no such alterations is reported (blinded for specific mutation) to the respective site of each subject. One trial site, Uppsala Akademiska Sjukhus (UAS), with three randomized subjects, has performed the tumor DNA sequencing and bioinformatics without assistance from Clinical Genomics or MEB. To enable randomization of a subject, each site enters the mutation status into the eCRF, which is regularly monitored (see Section 4.10), making errors in the mutation status variable highly unlikely. Data extracted from

MEB/UAS and from the eCRF on mutation status in the PI3K pathway will be compared, and in case of differences, the mutation status from MEB/UAS will be used in all analyses, even though randomization is based on mutation status from the eCRF (see Section 4.6 for details on the randomization procedure).[2] In case multiple tumor samples from the same patient have been analyzed, several reports are sent to site. If a subject has somatic alterations in PIK3CA (Mutation A) in one tumor sample, and other PIK3CA/PIK3R1/PTEN (Mutation B) in another, the PIK3CA (Mutation A) mutation status will be used in all analyses. Any discrepancies between mutation status in the eCRF and in data extracted from MEB/UAS will be clearly described.

4.9.7 Data on subjects withdrawing written informed consent

For subjects who, during the trial, withdraw their written informed consent, data collected up to the date of withdrawal will be used in descriptive tables and analyses, but no further data will be collected

4.10 Monitoring

Each site is monitored at regular time-intervals to ensure the site's compliance with the protocol, adherence to good clinical practice, completeness of the eCRFs, and consistency of the eCRF to the clinical records. The monitoring is performed by the Karolinska Trial Alliance (KTA) – a regulatory unit of the Karolinska University Hospital in Stockholm. When each randomized subject at a specific site has reached EoS and/or has 3 years of follow-up, KTA will close the site. The closing of most sites will occur during 2024.

4.11 Trial reporting

Results from the trial will be reported according to the CONSORT statements.[3]

5 General analysis considerations

5.1 Timing of analyses

The last subject to be randomized was entered into the trial July 19, 2021, meaning all subjects will have at least 3 years of follow-up on August 9, 2024, allowing for the visit window of 21 days. Analyses of the primary endpoint, and of secondary endpoints 1-3 and 6 will be performed as soon as possible after August 9, 2024. All sites need to be closed by KTA before any analyses can be performed, see Section 4.10 for details.

The analysis of secondary endpoints 4 and 5 (OS assessed at 5 years from randomization) will be possible from August 19, 2026, allowing for the 30-day visit window of Visit 16. Vital status and death date (if any) for subjects having reached EoS before visit 15 will have to be collected from sites before the analyses of secondary endpoints 4 and 5 can be conducted.

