#### 10.2.5 Follow-up period (Final visit 16 )

The follow-up period will start after the final treatment visit and ends after 2 years. The patient will visit the site or be contacted by phone at the end of the follow-up period i.e. after 2 years. A visit window of  $\pm 30$  days is allowed. Any other assessment e.g. endoscopic investigation that will be performed according to standard care will not be documented in the study.

The following assessments will be performed during the follow-up visit;

- Documentation of CEA (Optional), if not available a sample will be taken
- Review if there is any clinical suspicion of recurrence

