4.1 Trial description

The ALASCCA trial is a randomized, 2-arm, parallel group, double blind, multicenter, placebo-controlled, superiority clinical trial. CRC patients with a stage I-III (rectal cancer) or II-III (colon cancer) localized tumor with somatic alterations in the PIK3CA, PIK3R1, or PTEN genes are invited to participate in the randomized part of the trial.

CRC patients are screened for mutations in the PI3K signaling pathway, randomized, and provided with the investigational medical product (IMP) – ASA 160 mg or placebo – within three months from surgery. The IMP is to be taken daily for three years after randomization. Subjects treated with adjuvant chemotherapy, who, for medical reasons, should not receive ASA are allowed to start taking the IMP after termination of chemotherapy. Subjects are

allowed to pause treatment for up to 30 consecutive days to enable surgical procedures that should not be combined with ASA.

Subjects are contacted every three months until three years post randomization, with an additional contact five years after randomization. Computed tomography (CT) or magnetic resonance imaging (MRI) of the thorax and abdomen to detect CRC recurrence is performed at 1 year and 3 years after randomization.

Patients that are being treated regularly with ASA (>3 doses per week) at inclusion will not be randomized. However, these patients will be included in an observational arm – regardless of mutation status. Aims, endpoints, data collection, and analyses for the observational arm will be described in an amendment to this SAP.

The ALASCCA trial includes 33 hospitals across Sweden, Denmark, Finland, and Norway.

[figure not shown]

Figure 1. Study design of the randomized part of the ALASCCA trial

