4.8 Trial assessments

Written informed consent is given by the patient in the first screening visit, which takes place before or shortly after surgery (allowing for randomization to be performed within 12 weeks from surgery).

In the second screening visit, which takes place after surgery, inclusion and exclusion criteria are assessed in patients with tumors harboring somatic alterations in the PIK3CA, PIK3R1 or PTEN genes. Patients without such somatic alterations, and patients not fulfilling all inclusion criteria, or fulfilling at least one exclusion criteria are excluded from the trial. However, patients with regular use of ASA (>3 doses/week) fulfilling all other eligibility criteria, are included in an observational arm.

Randomization takes place in the third visit, in which the subject is also provided with IMP for 200 days. The treatment period begins at the randomization visit and ends after 3 years.

A phone contact is made with the subject three months from randomization, and thereafter every sixth month. Also, subjects visit their respective site every sixth month from randomization, i.e,. the subjects are in contact with the site every third months for three years. At the end of the follow-up period, five years from randomization, there is an additional visit or phone contact for subjects who have completed three years in the trial (up to and including Visit 15). The trial assessments, starting from randomization, are visualized in Figure 2, and described in detail in Table 4.

[figure not shown]

Figure 2. Time-line of trial assessments. The dice icon refers to Randomization, the phone icon to Phone contact, the human icon to Clinic visit, and the skeleton icon to clinic visit including examination with CT/MRI.

Table 4. Overview of trial assessments

Assessment/Visit	Random- ization (R)	First phone call	First site visit	Subsequent phone calls	Subsequent site visits	Final visit/phone call
Visit no.*	3	4	5	6, 8, 10, 12, 14	5, 7, 9, 11, 13, 15	16
Timepoint	0	3mo after R	6mo after R	Every 6mo after first phone call	Every 6mo after first site visit	5y from R
Visit/call window	-	±21 days	±21 days	±21 days	±21 days	±30 days
Provide with IMP	Yes		Yes		Yes	
Assess AEs		Yes	Yes	Yes	Yes	
Subject asked about compliance		Yes	Yes	Yes	Yes	
Remaining pill count			Yes		Yes	
Record concomitant medication		Yes	Yes	Yes	Yes	
CT/MRI of thorax and abdomen					Yes (visit 7 and 15 – 1y and 3y after R)**	

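### Five-year death and recurrence for subjects who complete 3 years rest on Visit 16 alone, because the planned 5-year registry and site retrieval is written only for early leavers

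*SAP*

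**What the plan says.** **Contacts.** SAP 4.1: "Subjects are contacted every three months until three years post randomization, with an additional contact five years after randomization". The last contact is for completers: SAP 4.8 says that at five years "there is an additional visit or phone contact for subjects who have completed three years in the trial". Protocol 10.2.5 describes the same single contact: "The patient will visit the site or be contacted by phone at the end of the follow-up period i.e. after 2 years". Protocol Figure 2 and SAP Table 4 show nothing between Visit 15 (month 36) and Visit 16 (month 60).

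**Sources of 5-year data.** SAP Table 5 has two rows. For subjects who completed 3 years the source of 5-year recurrence and death is the eCRF, in every country. For subjects who left early it is the SCRCR or the sites. SAP 4.9.4 repeats the split: "Endpoint variables assessed at 5 years from randomization for subjects leaving the trial before trial completion are not entered into the eCRF", and for these subjects the data "will be collected from SCRCR for Swedish subjects, and from each included site for subjects in Nordic countries outside of Sweden". SAP 5.1, on what must be done before the overall survival (OS) analysis, names the same group: "Vital status and death date (if any) for subjects having reached EoS before visit 15 will have to be collected from sites".

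**Censoring.** Under SAP 6.2.1 a subject not known to have died is censored when last known alive. Death dates may come from the end-of-study record, from Visit 16, or from separate collection from sites, with a reference back to Section 4.9.

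**Monitoring.** SAP 4.10: "When each randomized subject at a specific site has reached EoS and/or has 3 years of follow-up, KTA will close the site". Most closures are expected in 2024.

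**The concern.** Most subjects should complete 3 years, so for most of the trial 5-year vital status depends on one form being filled in after two years without a scheduled contact. If that form stays empty, the plan calls for no look-up for that subject, although it calls for one for every early leaver. A failed contact is more likely after a death than in a living patient, so the resulting censoring may be informative and some OS events may be lost.

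The two routes also do not divide the arms evenly if the treatment works. Recurrence is an end-of-study reason (SAP 4.8), so a subject with recurrence moves to the retrieval route. The arm with fewer recurrences has more completers, and therefore more subjects who depend on Visit 16.

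At stake are secondary endpoints 4 and 5 (5-year OS in mutation groups A and B) and the exploratory 5-year TTR. The primary endpoint is assessed at 3 years and is not touched.

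**Working it through.** The documents give no OS event rate, OS power or expected loss at Visit 16, so there is no planned figure to reproduce. The check sets the passages side by side and then illustrates size with stated assumptions.

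**1. Gap and dates.** Visit 15 to Visit 16: 60 − 36 = 24 months. Last randomisation 19 July 2021 + 5 years + 30 days = 18 August 2026, which agrees with SAP 5.1 (OS analysis possible from 19 August 2026). Randomisation ran from 7 July 2016 (SAP Table 7), so Visit 16 contacts run from mid-2021 to August 2026. At a site closed at the end of 2024, Visit 16 is still to come for subjects randomised after the end of 2019.

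**2. Sources side by side.**

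| Data | Main source | Backstop in the SAP |
|---|---|---|
| 3 years, completers | eCRF | Separate collection for all subjects; chart review if nothing is registered (4.9.4, Table 5) |
| 5 years, early leavers | SCRCR and/or sites | The retrieval is itself the source |
| 5 years, completers | eCRF (Visit 16) | None written |

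**3. Share of completers by arm.** Inputs from SAP 4.5.2: placebo 3-year recurrence 18%, RR 0.38, drop-out 10%. Assumption: drop-out is independent of recurrence.
- ASA recurrence: 0.18 × 0.38 = 0.068.
- Placebo completers: 0.90 × (1 − 0.18) = 0.74.
- ASA completers: 0.90 × (1 − 0.068) = 0.84.
- With no effect on recurrence (RR = 1), both arms would have 0.74.

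Death without recurrence, other cancer and adverse events also end participation, so the true shares would be lower.

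**4. Deaths that could be lost (illustration).** Assume 5-year mortality of 10%, 15% or 20% at constant hazard in 300 subjects of one mutation group. Then S3 = S5^(3/5), and deaths in years 3–5 are 300 × (S3 − S5):
- 10%: 300 × (0.9387 − 0.90) = 11.6 of 30
- 15%: 300 × (0.9071 − 0.85) = 17.1 of 45
- 20%: 300 × (0.8747 − 0.80) = 22.4 of 60

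Lost deaths = this number × share of completers × share unrecorded. Assume 10–20% are unrecorded.
- Completers 90% (drop-out as the only way to leave): from 11.6 × 0.9 × 0.1 = 1.0 to 22.4 × 0.9 × 0.2 = 4.0; at 15% mortality, 1.5 to 3.1.
- Completers 79% (mean of 74% and 84%): from 11.6 × 0.79 × 0.1 = 0.9 to 22.4 × 0.79 × 0.2 = 3.5.

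Both ranges are probably high for these rates. Completers are recurrence-free at Visit 15, so the whole-cohort hazard probably overstates their later deaths.

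**5. Effect on the survival estimate (illustration).** Let q be the risk of death between months 36 and 60, and m the fraction of those deaths censored at month 36. The Kaplan-Meier risk for the interval becomes q(1 − m)/(1 − qm). With S3 = 0.95 and q = 0.08, true 5-year survival is 0.95 × 0.92 = 0.874.
- m = 0.10: 0.072/0.992 = 0.073, and the estimate is 0.881.
- m = 0.25: 0.060/0.980 = 0.061, and the estimate is 0.892.

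Over S3 of 0.92–0.95, q of 4–12% and m of 10–50%, the overstatement is about 0.4 to 5.3 percentage points. This treats everyone alive at month 36 as dependent on Visit 16, so it is an upper figure for each m.

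**The case against.** **Visit 16 is not a patient questionnaire.** It is a site-entered record. SAP Table 4 lists death and its date among its items, and SAP 6.2.1 uses that date. A site that finds the patient has died can record it. This stands: an event is lost only if the form is left unfilled, and the documents do not say how often that happens.

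**Other text leaves room for other sources.** Protocol 10.9 imports long-term follow-up from the SCRCR without limiting it to early leavers. Protocol 10.10 puts registry coverage above 98%, and 24 of the 33 sites are Swedish. SAP 6.2.1 accepts a site-collected death date for any subject. This stands in part. It shows that the data can be had, but the later and more specific SAP text states who is retrieved at 5 years and leaves completers out. The 6.2.1 rule refers back to that text, and subjects outside Sweden are not in the SCRCR.

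**Closure by the monitor does not stop sites supplying data.** This is correct, since SAP 5.1 itself plans collection from sites. What remains is that no monitoring is described for Visit 16 data entered after closure. A reader might also infer that the preference in SAP 4.9 for the monitored eCRF fails here. That preference covers variables with several sources, and Table 5 gives this one a single source, so the argument does not apply.

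**The last-known-alive date may be later than month 36.** Sites supply the 3-year data only once their last subject reaches 3 years, so for subjects randomised early the date may come from a later chart entry. This softens the worst case for them. The death item in that collection is still limited to 3 years.

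**Treatment is blinded and the process is the same in both arms.** This is true, but blinding does not equalise the share of completers if recurrence differs.

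**Conclusion.** The point holds as a gap in the plan that may lose OS events. For 3-year completers the SAP states a restricted 5-year retrieval rule, with no counterpart to its own 3-year chart review. The consequence is possible, not certain: a completer with an empty Visit 16 is censored when last known alive, perhaps at month 36, and that censoring may be informative.

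The size cannot be derived from the documents. About 1 to 4 lost deaths per mutation group follows only from assumed mortality (10–20%), assumed non-recording (10–20%) and 90% completers, and is probably towards the high end for those rates. The 74% and 84% completer shares follow from the plan's own recurrence, RR and drop-out figures, given drop-out independent of recurrence.

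Two stronger readings are tempting and not supported:
- That deaths among completers will go unrecorded because a dead patient cannot be contacted. Visit 16 provides for recording a death.
- That the OS hazard ratio is biased in favour of ASA. Reliance on Visit 16 could differ by arm if ASA reduces recurrence. But the rate of unfilled forms is unknown, exits for adverse events could shift the shares the other way, and with no effect on recurrence the shares are equal.

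The change is worth making before the 2026 analysis. It does not affect the primary result.

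**What to change.** In SAP 4.9.4, Table 5, 5.1 and the OS derivation in 6.2.1:
- Extend the planned 5-year retrieval of death, recurrence and the dates last known alive and last known recurrence-free to all randomised subjects who have not withdrawn consent. Use the SCRCR for Swedish subjects and the existing site form elsewhere.
- Use it as the backstop when Visit 16 is missing and as a cross-check when it is present.
- Censor at the latest date known event-free from either source, capped at 5 years plus 30 days.
- Reconcile the sources: 4.9.4 names the SCRCR for Swedish early leavers, while 5.1 and the list of death dates in 6.2.1 speak only of sites.

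The cost is SAP wording, a somewhat larger registry extract, and a short form for the 33 − 24 = 9 sites outside Sweden. The registry link and the form are already in use, and the analysis is not possible before August 2026. The downside is a small amount of extra data work.
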